6.2 Exclusion Criteria

1. Previous use of a BTK inhibitor

*Patients enrolled in a previous version of this protocol who are still in their 12-week active treatment period with PRN1008 are eligible to continue treatment, initially with their current dose level, under this amended protocol for an additional 12 weeks, i.e. 24 weeks total, following review and signature of the EC approved patient's consent. Patients who completed **Part A** and did not discontinue the study due to a medical condition that might compromise safety assessments or for a PRN1008 related adverse event may be screened for entry under **Part B**.*

2. Pregnant or lactating women

3. ECG findings of QTc > 450 msec (males) or > 470 msec (females), poorly controlled atrial fibrillation (i.e. symptomatic patients or a ventricular rate above 100 beats/min on ECG), or other clinically significant abnormalities
4. A history of malignancy of any type, other than surgically excised non-melanoma skin cancers or in situ cervical cancer within 5 years before the day of dosing
5. Use of immunologic response modifiers with the following periods prior to Day 1: as concomitant therapy, other immunologic response modifiers not detailed in this exclusion apart from corticosteroids; *1 week*: cyclophosphamide; *4 weeks*: IVIG, Kinaret (anakinra) and Enbrel (etanercept); *12 weeks*: Remicade (infliximab), Humira (adalimumab), Simponi (golimumab), Orenzia (abatacept), Actemra (tocilizumab), Cimzia (certolizumab), Cosentyx (secukinumab), plasmapheresis; *6 months*: Rituxan/MabThera (rituximab), ofatumumab, any other anti-CD20 antibody, other long-acting biologics
6. More than 0.5 mg/kg of prednis(ol)one per day (“low dose corticosteroids”) within the two weeks prior to Day 1
7. Use of proton pump inhibitor drugs such as omeprazole and esomeprazole (it is acceptable to change patient to H2 receptor blocking drugs prior to the first dose of PRN1008)
8. Concomitant use of known strong-to-moderate inducers or inhibitors of CYP3A ([Appendix 2](#)) within 3 days or 5 half-lives (whichever is longer) of study drug dosing
9. Use of CYP3A-sensitive substrate drugs ([Appendix 3](#)) with a narrow therapeutic index within 3 days or 5 half-lives (whichever is longer) of study drug dosing including, but not limited to, alfentanil, astemizole, cisapride, cyclosporine, dihydroergotamine, ergotamine, fentanyl, pimozide, quinidine, sirolimus, tacrolimus, or terfenadine

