5.4.1 Primary Efficacy Endpoint

The primary efficacy endpoint is:

- The proportion of patients who are able to achieve CDA within 4 weeks (on or prior to Week 5 visit) of starting PRN1008 treatment **without** the need for doses of prednis(ol)one > 0.5 mg/kg

The Control of Disease Activity (CDA) responses are assessed at visits specified in the Schedule of assessments (Table 1). Types of CS other than prednis(ol)one are converted to dose-equivalent prednis(ol)one (see Section 5.4.2.3).

This is operationalized as meaning the first CDA is achieved on or before the Week 5 visit but after first dose of PRN1008, and will be summarized, by dose level to the Week 5 visit and overall in a table, using frequencies and percentages. In addition, two-sided 80% and 95% CIs (Confidence Intervals) of the response rate will be provided for each dose level and overall.

Patients who are able to achieve CDA between first dose of study drug and the Week 5 visit without prednis(ol)one >0.5 mg/kg on the date prior to the CDA will be considered as responders, even if the CDA status was not maintained or higher doses of prednis(ol)one were used after the first CDA. Patients who are not able to achieve CDA prior to or at the Week 5 visit or had prednis(ol)one >0.5 mg/kg on the date prior to CDA will be considered as non-responders. Patients whose CDA status is unknown at the Week 5 visit for whatever reason (including early termination before Week 5 visit) will be also considered as non-responders. Only systemic CSs (as defined by medication taken orally or intravenously) are to be used to evaluate the efficacy endpoints, topical CSs (including buccal CS) will not be counted.

The number and percentage of patients who meet the primary efficacy endpoint criteria will be tabulated by dose level and overall (all patients).

A sensitivity analysis using the Completer and PP population will be provided.

Panel plots will be provided for PDAI score over the study period for each patient. Dose level (mg/day) will also be plotted on the same figure. Lines for the steroid equivalent dose in mg/kg will be added to the plots. A total of 9 plots (3 x 3) will be fitted on one page.

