5.4.2 Secondary Efficacy Endpoints

5.4.2.1 CDA Responses

The number and percentage of patients who meet the criteria below will be tabulated by dose level and overall where the response first occurred and overall. 80% and 95% CIs will be calculated for the proportions using the Exact (Clopper-Pearson) method .

- 1) Cumulative incidence of patients able to achieve CDA by each visit
- 2) Cumulative incidence of patients able to achieve CDA by each visit on zero steroids.
- 3) Cumulative incidence of patients able to achieve CDA by each visit **with** the need for doses of prednis(ol)one of greater than 0.5 mg/kg
- 4) Cumulative incidence of patients able to achieve CDA by each visit **without** the need for doses of prednis(ol)one of greater than 0.5 mg/kg
- 5) Proportion of patients able to achieve CDA at each visit
- 6) Proportion of patients able to achieve CDA at each visit **with** the need for doses of prednis(ol)one of greater than 0.5 mg/kg
- 7) Proportion of patients able to achieve CDA at each visit **without** the need for doses of prednis(ol)one of greater than 0.5 mg/kg
- 8) Cumulative incidence of patients able to achieve CR by each visit
- 9) Cumulative incidence of patients able to achieve CR by each visit **with** the need for doses of prednis(ol)one of greater than 0.5 mg/kg
- 10) Cumulative incidence of patients able to achieve CR by each visit **without** the need for doses of prednis(ol)one of greater than 0.5 mg/kg
- 11) Proportion of patients able to achieve CR at each visit
- 12) Proportion of patients able to achieve CR at each visit **with** the need for doses of prednis(ol)one of greater than 0.5 mg/kg
- 13) Proportion of patients able to achieve CR at each visit **without** the need for doses of prednis(ol)one of greater than 0.5 mg/kg
- 14) Proportion of patients able to achieve a complete CR **with** the need for dose of prednis(ol)one of greater than 0.5 mg/kg within 24 weeks, i.e. on or prior to Week 25 visit
- 15) Proportion of patients able to achieve a complete response (CR) **without** prednis(ol)one of greater than 0.5 mg/kg within 24 weeks, i.e. on or prior to Week 25 visit

The CDA status, CR status, ECP status, and Relapse status by visit, by patient will be presented in a listing.

Duration of CR will be summarized and listed, and is defined by the longest period of consecutive visits in CR (last known CR date – first known CR date + 1). Each subject will only have one CR duration as a result.

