5.4.2.2 Time-to-Event

The following time-to-event analyses will be performed by dose level and overall for events occurred after date of first study drug dosing:

- a) Time to first CDA
- b) Time to first CR
- c) Time to first ECP
- d) Time to first relapse (after CDA has been achieved, as per the definition of relapse) after first dose of study drug
- e) Time to first increase in PDAI

For each event listed above, the number of days to the event will be calculated as:

(Date of first occurrence of event – Date of first study drug dosing of the dose level where the event is observed) + 1

The number of days to first occurrence of each event (a to d) will be summarized by descriptive statistics for each dose level and overall.

Patients who did not achieve the specific event are censored at the last day in a dose level or date of study completion/discontinuation.

Kaplan-Meier estimates of quartiles in days and their associated 80% and 95% CI will be calculated by using the LOGLOG transformation. Minimum and maximum survival times in days as well as number of the patients and the probability of experiencing the event on or before specific date will be provided in a table.

A sensitivity analysis using the Completer and PP populations will be provided.

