Table B.14.2.1.5.3 Proportion of patients Achieved CDA at or Prior to Week 5 without prednis(ol)one >0.5 mg/kg – Subgroup – Pemphigus History (PP Population)

Note: Subgroups are: ‘Newly diagnosed (\leq 6 months from screening)’, ‘Relapsed (>6 months from screening)’

Additional footnote: Newly diagnosed is defined as subjects who were diagnosed at most 6 months prior to date of screening, otherwise the subject is relapsed.

Table B.14.2.1.6.1 Proportion of patients Achieved CDA at or Prior to Week 5 without prednis(ol)one >0.5 mg/kg – Subgroup – Baseline Pemphigus Anti-DSG Profile (mITT Population)

Table B.14.2.1.6.2 Proportion of patients Achieved CDA at or Prior to Week 5 without prednis(ol)one >0.5 mg/kg – Subgroup – Baseline Pemphigus Anti-DSG Profile (Completer Population)

Table B.14.2.1.6.3 Proportion of patients Achieved CDA at or Prior to Week 5 without prednis(ol)one >0.5 mg/kg – Subgroup – Baseline Pemphigus Anti-DSG Profile (PP Population)

Note: Subgroups are: ‘Pemphigus Vulgaris (PV)’, ‘Pemphigus foliaceus (PF)’ and ‘Negative anti-DSG profile’

Table B.14.2.1.7.1 Proportion of patients Achieved CDA at or Prior to Week 5 without prednis(ol)one >0.5 mg/kg – Subgroup Analysis – Baseline Pemphigus Severity (mITT Population)

Table B.14.2.1.7.2 Proportion of patients Achieved CDA at or Prior to Week 5 without prednis(ol)one >0.5 mg/kg – Subgroup Analysis – Baseline Pemphigus Severity (Completer Population)

Table B.14.2.1.7.3 Proportion of patients Achieved CDA at or Prior to Week 5 without prednis(ol)one >0.5 mg/kg – Subgroup Analysis – Baseline Pemphigus Severity (PP Population)

Note: Subgroups are: ‘Mild at Baseline’, ‘Moderate at Baseline’

Additional footnote: Based on PDAI total activity score. For newly diagnosed patients: Mild is 0 to 14 and Moderate is 15 to 44. For relapsed patients: Mild is 0 to 8 and Moderate is 9 to 24.

Table B.14.2.2.1.1 Cumulative Incidence of Patients Achieved CDA by Visit – Cumulative Incidence (mITT Population)

Visit	Achieved CDA	400 mg QD (N = n)	400 mg BID (N = n)	600 mg BID (N = n)	Overall (N = n)
SCREENED	N achieved (%)	x (x.x)	x (x.x)	x (x.x)	x (x.x)
	- 80% CI	x.xx, x.xx	x.xx, x.xx	x.xx, x.xx	x.xx, x.xx
	- 95% CI	x.xx, x.xx	x.xx, x.xx	x.xx, x.xx	x.xx, x.xx
WEEK 1 DAY 1	Cumulative N achieved (%)	x (x.x)	x (x.x)	x (x.x)	x (x.x)
	- 80% CI	x.xx, x.xx	x.xx, x.xx	x.xx, x.xx	x.xx, x.xx
	- 95% CI	x.xx, x.xx	x.xx, x.xx	x.xx, x.xx	x.xx, x.xx
WEEK 1 DAY 2	Cumulative N achieved (%)	x (x.x)	x (x.x)	x (x.x)	x (x.x)

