	- 80% CI	x.xx, x.xx	x.xx, x.xx	x.xx, x.xx	x.xx, x.xx
	- 95% CI	x.xx, x.xx	x.xx, x.xx	x.xx, x.xx	x.xx, x.xx
WEEK 3 DAY 15	...etc...				
...etc..					
WEEK 29 DAY 197	Cumulative N achieved (%)				x (x.x)
	- 80% CI				x.xx, x.xx
	- 95% CI				x.xx, x.xx

Percentages are based on the number of patients in each dose group and overall.
 Patients are classified into different dose levels according to the dose they received prior to achieving CDA.
 Confidence Intervals are based on the Exact (Clopper-Pearson) method.
 Secondary efficacy endpoint: Proportion of patients who achieved CDA at each visit.
 Program: <program name (date, time)>, Path: <path>

Table B.14.2.2.1.2 Cumulative Incidence of Patients Achieved CDA by Visit (Completer Population)

Table B.14.2.2.1.3 Cumulative Incidence of Patients Achieved CDA by Visit (PP Population)

Table B.14.2.2.2.1 Cumulative Incidence of Patients Achieved CDA by Visit without Corticosteroids (mITT Population)

Table B.14.2.2.2.2 Cumulative Incidence of Patients Achieved CDA by Visit without Corticosteroids (Completer Population)

Table B.14.2.2.2.3 Cumulative Incidence of Patients Achieved CDA by Visit without Corticosteroids (PP Population)

Table B.14.2.2.3.1 Cumulative Incidence of Patients Achieved CDA by Visit with prednis(ol)one >0.5 mg/kg (mITT Population)

Table B.14.2.2.3.2 Cumulative Incidence of Patients Achieved CDA by Visit with prednis(ol)one >0.5 mg/kg (Completer Population)

Table B.14.2.2.3.3 Cumulative Incidence of Patients Achieved CDA by Visit with prednis(ol)one >0.5 mg/kg (PP Population)

Table B.14.2.2.4.1 Cumulative Incidence of Patients Achieved CDA by Visit without prednis(ol)one >0.5 mg/kg – Cumulative Incidence (mITT Population)

Table B.14.2.2.4.2 Cumulative Incidence of Patients Achieved CDA by Visit without prednis(ol)one >0.5 mg/kg – Cumulative Incidence (Completer Population)

Table B.14.2.2.4.3 Cumulative Incidence of Patients Achieved CDA by Visit without prednis(ol)one >0.5 mg/kg (PP Population)

Table B.14.2.2.5.1 Proportion of patients Achieved CDA by Visit (mITT Population)

Visit	Achieved CDA	400 mg QD (N = n)	400 mg BID (N = n)	600 mg BID (N = n)	Overall (N = n)
SCREENED	N achieved (%)	x (x.x)	x (x.x)	x (x.x)	x (x.x)
	- 80% CI	x.xx, x.xx	x.xx, x.xx	x.xx, x.xx	x.xx, x.xx
	- 95% CI	x.xx, x.xx	x.xx, x.xx	x.xx, x.xx	x.xx, x.xx
WEEK 1 DAY 1	N achieved (%)	x (x.x)	x (x.x)	x (x.x)	x (x.x)
	- 80% CI	x.xx, x.xx	x.xx, x.xx	x.xx, x.xx	x.xx, x.xx

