	- 95% CI	x.xx, x.xx	x.xx, x.xx	x.xx, x.xx	x.xx, x.xx
WEEK 1 DAY 5					
...etc..					
WEEK 29 DAY 197					

Percentages are based on the number of patients in each dose group and overall.
 Patients are classified into different dose levels according to the dose they received prior to achieving CDA.
 Confidence Intervals are based on the Exact (Clopper-Pearson) method.
 Secondary efficacy endpoint: Proportion of patients who achieved CDA at each visit.
 Program: <program name (date, time)>, Path: <path>

Table B.14.2.2.5.2 Proportion of patients Achieved CDA by Visit (Completer Population)

Table B.14.2.2.5.3 Proportion of patients Achieved CDA by Visit (PP Population)

Table B.14.2.2.6.1 Proportion of patients Achieved CDA with prednis(ol)one >0.5 mg/kg by Visit (mITT Population)

Table B.14.2.2.6.2 Proportion of patients Achieved CDA with prednis(ol)one >0.5 mg/kg by Visit (Completer Population)

Table B.14.2.2.6.3 Proportion of patients Achieved CDA with prednis(ol)one >0.5 mg/kg by Visit (PP Population)

Table B.14.2.2.7.1 Proportion of patients Achieved CDA without prednis(ol)one >0.5 mg/kg by Visit (mITT Population)

Table B.14.2.2.7.2 Proportion of patients Achieved CDA without prednis(ol)one >0.5 mg/kg by Visit (Completer Population)

Table B.14.2.2.7.3 Proportion of patients Achieved CDA without prednis(ol)one >0.5 mg/kg by Visit (PP Population)

Table B.14.2.2.8.1 Cumulative Incidence of Patients Achieved CR by Visit – Cumulative Incidence (mITT Population)

Visit	Achieved CR	400 mg QD (N = n)	400 mg BID (N = n)	600 mg BID (N = n)	Overall (N = n)
SCREENED	N achieved (%)	x (x.x)	x (x.x)	x (x.x)	x (x.x)
	- 80% CI	x.xx, x.xx	x.xx, x.xx	x.xx, x.xx	x.xx, x.xx
	- 95% CI	x.xx, x.xx	x.xx, x.xx	x.xx, x.xx	x.xx, x.xx
WEEK 1 DAY 1	Cumulative N achieved (%)	x (x.x)	x (x.x)	x (x.x)	x (x.x)
	- 80% CI	x.xx, x.xx	x.xx, x.xx	x.xx, x.xx	x.xx, x.xx
	- 95% CI	x.xx, x.xx	x.xx, x.xx	x.xx, x.xx	x.xx, x.xx
WEEK 1 DAY 2	Cumulative N achieved (%)	x (x.x)	x (x.x)	x (x.x)	x (x.x)
	- 80% CI	x.xx, x.xx	x.xx, x.xx	x.xx, x.xx	x.xx, x.xx
	- 95% CI	x.xx, x.xx	x.xx, x.xx	x.xx, x.xx	x.xx, x.xx
WEEK 3 DAY 15	...etc...				
...etc..					
WEEK 29 DAY 197	Cumulative N achieved (%)				x (x.x)
	- 80% CI				x.xx, x.xx
	- 95% CI				x.xx, x.xx

Percentages are based on the number of patients in each dose group and overall.
 Patients are classified into different dose levels according to the dose they received prior to achieving CR.

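### Part B's cumulative CDA tables begin counting before the first dose, so disease control already present at entry could be carried forward as response

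*SAP*

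**What the plan says.** Part B SAP Section 5.4.2.1 lists as item 1 "Cumulative incidence of patients able to achieve CDA by each visit". Items 2 to 4 split this by steroid use, and items 8 to 10 are the CR counterparts. None is limited to responses after the first dose.

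The shell for Table B.14.2.2.1.1 (Section 6) starts with a SCREENED row giving the number achieved. The next row, WEEK 1 DAY 1, is labelled "Cumulative N achieved". Both are filled in all three dose columns and in Overall. Only the off-drug Week 29 row leaves the dose columns blank. Tables B.14.2.2.2.x to .4.x are given as titles under this shell, and the CR shell (B.14.2.2.8.1) has the same rows. A footnote says: "Patients are classified into different dose levels according to the dose they received prior to achieving CDA".

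Other analyses do carry a post-dose condition. For the primary endpoint, Section 5.4.1 says: "This is operationalized as meaning the first CDA is achieved on or before the Week 5 visit but after first dose of PRN1008". Section 5.4.2.2 runs its analyses "for events occurred after date of first study drug dosing". The Part A cumulative shell (Table 14.2.2.4.4.1) begins at Week 3 Day 15, and its footnote counts responses reached during study treatment.

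**The concern.** CDA is a low bar at entry. Section 3.4.7 of the Part B SAP asks only that new lesions have stopped and existing ones have begun to heal. It dates CDA at its first occurrence, with no lower limit at the first dose. The protocol admits Part B patients with a PDAI of 8 or more on up to 0.5 mg/kg of prednis(ol)one (Sections 6.1 and 6.2). It allows up to 28 days between screening and dosing (Section 7) and describes the disease as acutely responsive to corticosteroids (Section 1.2). A patient could therefore begin to settle on background steroid between Screening and Day 1.

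In a cumulative table that patient is a responder from the Day 1 row onwards. The trial has no comparator in which the same pre-existing control would appear. The cumulative rates could then exceed the primary and Kaplan-Meier results for the same patients. They would also be built differently from Part A's, which the protocol allows to be combined with Part B where appropriate (Section 11.9.1).

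**Working it through.** **The plan's own figure.** Part B SAP Section 2.3 gives an 80% confidence interval of ±13% for a 50% rate with 25 patients. The normal approximation gives 1.2816 × √(0.5 × 0.5 / 25) = 1.2816 × 0.1 = 0.128, so the figure reproduces. It serves here only as a yardstick.

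**One patient traced through the rules.** Take a hypothetical patient with CDA Yes at Day 1 pre-dose and No at every visit after dosing.

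- Primary endpoint (5.4.1): non-responder, because there is no CDA after the first dose.
- Time to first CDA (5.4.2.2): no event, censored.
- At-visit CDA table (B.14.2.2.5.1): Yes at Day 1, No afterwards.
- Cumulative CDA tables (B.14.2.2.1.x and whichever steroid variants apply): Yes at Day 1 and in every later row.
- Dose column: none applies, because no dose came before the CDA. The patient still counts in Overall.

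Item 4 of 5.4.2.1 (cumulative CDA without prednis(ol)one above 0.5 mg/kg) is a useful cross-check. Its Week 5 row uses the same population, cut-off and steroid threshold as the primary endpoint, so the two should agree. This patient, if on low-dose steroid, counts in one and not in the other.

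**Size per patient.** The number of patients in CDA before dosing is not given, so k is an assumption. Take n = 25 (planned per Part) and, for illustration, 12 post-dose responders. Suppose k further patients had CDA only before dosing. The displayed rate is (12 + k)/25, with exact 80% intervals as planned for these tables:

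- k = 0: 12/25 = 48% (33.8 to 62.5)
- k = 1: 13/25 = 52% (37.5 to 66.2)
- k = 2: 14/25 = 56% (41.3 to 69.9)
- k = 3: 15/25 = 60% (45.2 to 73.5)

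Each such patient adds 1/25 = 4 points, so one to three add 4 to 12 points, against a stated precision of ±13. Under the same assumption, k/25 is a floor below which no later row can fall.

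**Patients in CDA at entry who stay in CDA.** These would be counted after dosing under either rule, so correcting the layout does not change their contribution from Week 3 on. Whether they should be credited to PRN1008 is a separate question, answered by leaving them out of numerator and denominator. If k of the 12 responders are of this kind, the rate becomes (12 − k)/(25 − k): 11/24 = 45.8%, 10/23 = 43.5% and 9/22 = 40.9% for k = 1, 2 and 3. If instead the k patients had CDA only before dosing, it is 12/(25 − k): 50.0%, 52.2% and 54.5%.

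**The case against.** The strongest reply is that the early rows are a generic visit list. They include Week 1 Day 2, when no PDAI or ABSIS is scheduled. The at-visit CDA shell prints a Week 1 Day 5 row, which is not a study visit. Section 6 says the shells may be adjusted. Section 4.7 presents the cumulative endpoints as taken over from Part A, where the shell counted on-treatment responses, and the dose footnote presupposes that a dose came first. All this suggests that on-treatment counting was intended. But Section 5.4.2.1 contains no rule to fall back on if the shell is programmed as drawn. The blank dose cells at Week 29 also show that rows were fitted to exposure, while the pre-dose rows stayed filled. Part B does not repeat Part A's carry-forward sentence; here it follows from the word cumulative.

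The case is also narrow. Patients must be newly diagnosed or relapsing, and Section 3.4.7 does not allow CDA to be Yes when relapse is Yes. A patient coded as in relapse at Day 1 cannot be the problem case. The at-visit tables already print Screening and Day 1 status, so a careful reader could see any pre-dose count.

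A reader might infer more than the documents support:

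- **That CR is inflated to the same degree.** CR needs all lesions healed, which is hardly compatible with a PDAI of at least 8 at entry.
- **That patients continuing from Part A enter already controlled.** The protocol does let in those "still in their 12-week active treatment period with PRN1008 are eligible to continue treatment", but their handling belongs to SAP Section 3.2.8, whose text was not available for this review. The point does not depend on them.
- **That pre-dose CDA is known to have occurred.** Listing B.16.2.6.10 shows status fields at Screening and Day 1, but the mock entries there are No.

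**Conclusion.** The concern holds for the cumulative CDA tables. As laid out, they count disease control recorded before the first dose and carry it to every later visit. This conflicts with the post-dose conditions in Sections 5.4.1 and 5.4.2.2 and departs from Part A without being listed in Section 4.7.

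The excess is 1/n for each patient in CDA before dosing and not otherwise counted: 4 points at n = 25. It lasts until that patient regains CDA on treatment, or to the end if that never happens. The one-to-three range is an assumption, and the true number may be zero.

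It would be wrong to conclude that the primary endpoint or the Kaplan-Meier analyses are biased by this layout, since both carry their own post-dose condition. The CR tables should be aligned for consistency, but little change is expected in new entrants.

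**What to change.** In Section 5.4.2.1 and the cumulative shells (B.14.2.2.1.x to .4.x, and .8.x to .10.x for CR):

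- Count a patient from the first post-dose visit at which CDA (or CR) status is Yes, whatever onset date is recorded. A rule based on the onset date would not do: CDA is dated at its first occurrence, so a patient in continuous CDA from entry might never be counted.
- Make Week 3 Day 15 the first cumulative row, as in Part A.
- Leave Screening and Day 1 status to the existing at-visit tables, which need no new baseline line.
- Repeat the cumulative CDA rates and the Week 5 CDA rate with patients recorded as CDA Yes at Day 1 pre-dose removed from numerator and denominator.
- List the change in Section 4.7.

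The cost is a sentence, a shell edit and one extra sensitivity table, all from status already collected. The cumulative rates may come out slightly lower.

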2.2 Study Design

This is a Phase 2, open-label, pilot cohort study to evaluate the safety, clinical activity, pharmacodynamics, and pharmacodynamics of PRN1008 in patients with newly diagnosed or relapsing PV. An open-label design was chosen for several reasons: PV does not spontaneously remit so there is no placebo effect to account for; clinicians need to know when to use rescue CSs, if necessary, in a timely manner; and lastly, the pilot nature of the investigation itself is best explored in an open-label fashion.

Up to 28 days before enrollment in the study, patients will be required to sign an informed consent form, after which screening assessments will be carried out. Patients must fulfill all entry criteria to be enrolled into the study. Patients who fail to meet the entry criteria may be rescreened at the discretion of the Investigator. Up to 25 male or female patients with newly diagnosed (i.e., naïve to an effective induction treatment regimen) or relapsing, biopsy-proven, mild or moderate PV patients (Pemphigus Disease Activity Index [PDAI] 8 to 45) to enrolled into each parts of the study.

In Part A, the initial dosing was 400 mg twice daily (bid). The duration of study therapy was 12 weeks starting on Day 1 and ending on study Day 84 (total duration of individual subject participation is 28 weeks), with follow-up visits (off-treatment) until Week 29.

In Part B, the initial dosing is 400 mg once daily (qd), with intra-patient dose escalation to 400 mg bid allowed at or after the Week 3 visit for insufficient clinical response (and then again to 600 mg bid if necessary at or after the Week 5 visit). The duration of study therapy is 24 weeks starting on Day 1 and ending on study Day 169, with a follow-up visit (off-treatment) on Day 197 (Week 29). The total duration of individual subject participation is approximately 32 weeks.

Dose Escalation Rules Part B

Current Dose	Inadequate Clinical Response* Dose-Escalation Rules
400 mg qd	Increase to 400 mg bid (allowed at Week 3 visit or later)**
400 mg bid	Increase to 600 mg bid (allowed at Week 5 visit or later)**
600 mg bid	No dose increase possible.

* Investigator discretion: Generally, clinical response is shown by some improvement seen in first 2 weeks with CDA achieved by the Week 5 visit

** Unless tolerability issues preclude dose-escalation

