5.4 Efficacy Analyses

The mITT population will be used for all efficacy analyses. For analyses at a particular study drug dose, all patients who received that dose at least once will be included. In addition, for selected analyses, where specified, the Completer and PP population will be used.

The descriptive statistics will be done by dose level and overall for all study visits, unless specified otherwise. All binomial confidence intervals for efficacy analyses will use the Exact (Clopper-Pearson) method. Patient data listings will be listed by starting dose, patient, dose level and study visit.

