 Confidence Intervals are based on the Exact (Clopper-Pearson) method.
 Secondary efficacy endpoint: Proportion of patients who achieved CDA at each visit.
 Program: <program name (date, time)>, Path: <path>

Table B.14.2.2.8.2 Cumulative Incidence of Patients Achieved CR by Visit – Cumulative Incidence (Completer Population)

Table B.14.2.2.8.3 Cumulative Incidence of Patients Achieved CR by Visit – Cumulative Incidence (PP Population)

Table B.14.2.2.9.1 Cumulative Incidence of Patients Achieved CR with prednis(ol)one >0.5 mg/kg by Visit – Cumulative Incidence (mITT Population)

Table B.14.2.2.9.2 Cumulative Incidence of Patients Achieved CR with prednis(ol)one >0.5 mg/kg by Visit – Cumulative Incidence (Completer Population)

Table B.14.2.2.9.3 Cumulative Incidence of Patients Achieved CR with prednis(ol)one >0.5 mg/kg by Visit – Cumulative Incidence (PP Population)

Table B.14.2.2.10.1 Cumulative Incidence of Patients Achieved CR without prednis(ol)one >0.5 mg/kg by Visit – Cumulative Incidence (mITT Population)

Table B.14.2.2.10.2 Cumulative Incidence of Patients Achieved CR without prednis(ol)one >0.5 mg/kg by Visit – Cumulative Incidence (Completer Population)

Table B.14.2.2.10.3 Cumulative Incidence of Patients Achieved CR without prednis(ol)one >0.5 mg/kg by Visit – Cumulative Incidence (PP Population)

Table B.14.2.2.11.1 Proportion of patients Achieved CR by Visit (mITT Population)

Visit	Achieved CR	400 mg QD (N = n)	400 mg BID (N = n)	600 mg BID (N = n)	Overall (N = n)
SCREENED	N achieved (%)	x (x.x)	x (x.x)	x (x.x)	x (x.x)
	- 80% CI	x.xx, x.xx	x.xx, x.xx	x.xx, x.xx	x.xx, x.xx
	- 95% CI	x.xx, x.xx	x.xx, x.xx	x.xx, x.xx	x.xx, x.xx
WEEK 1 DAY 1	N achieved (%)	x (x.x)	x (x.x)	x (x.x)	x (x.x)
	- 80% CI	x.xx, x.xx	x.xx, x.xx	x.xx, x.xx	x.xx, x.xx
	- 95% CI	x.xx, x.xx	x.xx, x.xx	x.xx, x.xx	x.xx, x.xx
WEEK 1 DAY 2					
...etc..					
WEEK 29 DAY 197					

Percentages are based on the number of patients in each dose group and overall.
 Patients are classified into different dose levels according to the dose they received prior to achieving CDA.
 Confidence Intervals are based on the Exact (Clopper-Pearson) method.
 Secondary efficacy endpoint: Proportion of patients who achieved CDA at each visit.
 Program: <program name (date, time)>, Path: <path>

Table B.14.2.2.11.2 Proportion of patients Achieved CR by Visit (Completer Population)

Table B.14.2.2.11.3 Proportion of patients Achieved CR by Visit (PP Population)

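### The Part B table of complete remission by visit carries CDA footnotes, so its dose grouping contradicts Section 5.4.2.1 and the other CR shells

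*SAP*

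**What the plan says.** Table B.14.2.2.11.1 in Section 6 of the Part B SAP is titled and labelled as CR by visit. Its dose footnote is "Patients are classified into different dose levels according to the dose they received prior to achieving CDA", and its endpoint line is "Secondary efficacy endpoint: Proportion of patients who achieved CDA at each visit". The CDA-by-visit shell, Table B.14.2.2.5.1, has the same two lines.

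Other parts of the SAP use a different rule for CR. Section 5.4.2.1 lists CR at each visit (items 11 to 13) among the endpoints that "will be tabulated by dose level and overall where the response first occurred and overall". Shells .8.1 (cumulative CR), .14.1 (CR by Week 25) and .16.1 (duration of CR) each state "Patients are classified into different dose levels according to the dose they received prior to achieving CR".

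On who belongs in a dose column, Section 5.4 says: "For analyses at a particular study drug dose, all patients who received that dose at least once will be included". Section 2.2 gives the ladder: 400 mg qd, then 400 mg bid from the Week 3 visit, then 600 mg bid from the Week 5 visit, for inadequate clinical response.

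**The concern.** A shell footnote tells the programmer how to build the grouping variable, and it prints under the finished table. Here it attaches a CR to the dose that preceded a different and usually earlier response. Section 3.4.7 requires CDA to be present whenever CR is, so first CDA falls at or before first CR. If doses only rise, the dose before CDA can equal the dose before CR or be lower, but never higher. Any misplacement therefore runs one way, towards the lower dose.

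That matters because Part B starts patients on 400 mg qd to see whether a once-daily dose is clinically effective (protocol Sections 2.1 and 2.2). The dose columns are what a reader will consult on that question.

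**Working it through.** The plan has no figure of its own on this point, so the check is a comparison of texts followed by an enumeration.

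**Step 1. The rules side by side.**

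| Place in Part B SAP | Response tabulated | Dose classification | Endpoint line names |
|---|---|---|---|
| Shell .5.1 | CDA by visit | before CDA | CDA |
| Shell .11.1 | CR by visit | before CDA | CDA |
| Shell .8.1 | cumulative CR | before CR | CDA |
| Shell .14.1 | CR by Week 25 | before CR | CR, with a Week 5 reference left in |
| Shell .16.1 | duration of CR | before CR | none |
| Section 5.4.2.1, items 11 to 13 | CR at each visit | level where the response first occurred | CR |

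Shell .11.1 is the only CR shell with a dose footnote that points to CDA.

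**Step 2. When the two rules differ.** The inputs are the three-step ladder in Section 2.2 and the CDA-before-CR ordering from Section 3.4.7. Footnote column = dose at first CDA. Section 5.4.2.1 column = dose at first CR.

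| Dose at first CDA | Dose at first CR | .11.1 footnote | Section 5.4.2.1 | Same column? |
|---|---|---|---|---|
| 400 qd | 400 qd | 400 qd | 400 qd | yes |
| 400 qd | 400 bid | 400 qd | 400 bid | no |
| 400 qd | 600 bid | 400 qd | 600 bid | no |
| 400 bid | 400 bid | 400 bid | 400 bid | yes |
| 400 bid | 600 bid | 400 bid | 600 bid | no |
| 600 bid | 600 bid | 600 bid | 600 bid | yes |

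Three of the six pairs change column. Two of those land in 400 mg qd and one in 400 mg bid. These are counts of possible paths, not of patients. Someone who escalates before first CDA and stays on that dose until CR is placed identically by both rules.

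**Step 3. Tables involved.** Three endpoints (.11, .12, .13) in three populations (mITT, Completer, PP) give 3 × 3 = 9 tables. Only .11.1 has a written shell. That the other eight inherit its footnotes is an inference.

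**Step 4. Scale per patient.** Under Section 5.4 an escalated patient stays in the denominator of every dose received, so a misplaced CR moves a numerator only. Assume 25 patients in the 400 mg qd column, the planned size per Part in Section 2.3. Each misplaced CR present at a given visit then adds 1/25 = 4 percentage points to that column, and k of them add 4k points: 0 for k = 0, 4 for k = 1, 8 for k = 2, 16 for k = 4. The column that loses the CR falls by 1/n, where n is the number who received that dose. The documents supply neither k nor n for the higher doses, so these figures set a scale and are not an estimate.

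**The case against.** The strongest reply is that this is a copying slip and not an analysis decision. Section 5.4.2.1 and three CR shells give the intended rule, and stray lines recur nearby: .8.1 has the CDA endpoint line, and .14.1 has a CDA, Week 5 row label. Section 6 says the shells set layout and may be adjusted. The text of Section 3.3 (Treatment Groups), listed in the contents, is not in the copy available, so a governing dose rule there cannot be excluded. Part B does no hypothesis testing. CR by dose also appears in .8 to .10 and .14 to .16, and Listings B.16.2.6.1 and B.16.2.6.10 print the dose beside CR status, so a misplaced remission could be traced.

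Most of this stands, and it limits the weight of the point. It does not remove the defect: the sections that can be read give no precedence of body text over shells, and a table programmed correctly would still print a wrong description of its groups and endpoint.

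A reader might infer something stronger, that remissions reached after escalation will be reported under 400 mg qd and inflate its CR rate. The documents do not support that. It needs the footnote to be followed against Section 5.4.2.1, and it needs CDA on qd, then escalation, then CR. Escalation is for inadequate response, and Section 2.2 adds: "Generally, clinical response is shown by some improvement seen in first 2 weeks with CDA achieved by the Week 5 visit". Many escalations should therefore come before CDA, where the rules agree. Escalation after CDA, for instance after a relapse, remains possible because timing is open-ended and at the investigator's discretion.

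**Conclusion.** The point holds as an internal contradiction in the programming specification. Followed literally, the .11.1 footnotes would put some CRs in a lower dose column than Section 5.4.2.1 and .8.1 would, and the table would name the wrong endpoint. The effect is confined to the dose columns of one descriptive secondary endpoint family. Its size cannot be computed from the documents.

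The direction rests on two assumptions. First, the footnote is read as first CDA; if a second CDA after relapse were used, some of these patients would be placed correctly. Second, doses only move up the ladder; the adverse-event summary shell allows for dose reductions, and a reduction between CDA and CR would shift a patient the other way.

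**What to change.** In Tables B.14.2.2.11.1-3, and explicitly in .12.1-3 and .13.1-3, change the dose footnote to the dose received prior to achieving CR, in line with Section 5.4.2.1 and .8.1. Change the endpoint line to CR at each visit, and correct the endpoint line of .8.1 from CDA to CR. The stray CDA and Week 5 labels in .14.1 can be cleared in the same pass. The cost is footnote wording and a check of one grouping variable. No new data are needed.
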